9.6.3 Management of Diabetes Medication

If subjects require addition of therapy with insulin, SFUs, GLP-1 receptor agonists, or SGLT inhibitors during the study, investigators should discontinue these subjects from the study, making all reasonable attempts to collect ABPM and assessments that are scheduled to occur at study completion prior to stopping study drug and changing these concurrent therapies.

9.6.4 Documentation of Concomitant Medication Use

All concomitant medications, including OTC products and nutritional/herbal supplements, must be listed on the appropriate case report form (CRF) at study entry. Any changes in concomitant medication use during the course of the study must also be noted on the appropriate CRF.

10.0 STUDY PROCEDURES

A schedule of study activities by visit are presented in [Appendix 1](#). For baseline and end of study ABPM visits, when possible, subjects should come in on the same day of the week to minimize within-subject variability. A detailed list of these activities is provided below.

10.1 Screening (Visit 1)

A schedule of study activities by visit is presented in [Appendix 1](#). A detailed list of these activities is provided below.

The following activities will take place at Screening (within 4 weeks of Baseline):

- Obtain written informed consent;
- Obtain demographics (including age, gender, race, and ethnicity) and medical history;
- Assess inclusion/exclusion criteria;
- Obtain body weight and height and calculate BMI. If a subject does not meet the BMI criterion for inclusion into the study, no further screening procedures should be undertaken;
- Perform a physical examination;
- Obtain vital signs (blood pressure, heart rate, respiration rate and temperature);
- Record prior and concomitant medications;
- Obtain blood sample for chemistry (full panel), hematology, lipids, HbA1c, TSH, HIV, HIV, and HBsAg; and urine sample for cotinine, urinalysis, and onsite urine drug screen. Refer to [Appendix 1](#) and [Table 2](#) for a listing of specific tests;
- Perform urine pregnancy test (women of childbearing potential [WOCBP] only) and remind subject about contraception. If the subject is pregnant, no further screening procedures should be performed;
- Perform 12-lead electrocardiogram (ECG);
- Enter screened subject into EDC/RTSM; and
- Schedule the Randomization visit within 4 weeks (+3 days).

10.2 Baseline/Randomization (Visit 2, Week 0/Beginning of Titration)

The following activities will take place at Visit 2A (first day of 2-day visit):

- Assess inclusion/exclusion criteria (applicable criteria referencing the baseline visit);
- Obtain body weight;
- Obtain vital signs (blood pressure, heart rate, respiration rate and temperature);
- Record any adverse events reported or observed;
- Record any changes in concomitant medications;
- Perform a urine pregnancy test (WOCBP only) and remind subject about contraception. If the subject is pregnant, she will not qualify for the study;
- Set up 24-hr ABPM monitoring equipment, and initiate monitoring;
- Provide subject with instructions for proper handling of ABPM device and remind the subject to return to the clinic in 24 hours to complete evaluation.

The following activities will take place at Visit 2B (second day of 2-day visit):

- Record any adverse events reported or observed;
- Record any changes in concomitant medications;

- End 24-hr ABPM monitoring, disconnect devices, and upload data;
- Contact EDC/RTSM to obtain randomization assignment for subject upon verifying successful ABPM; if verification of successful ABPM cannot be made, repeat 24-hr ABPM setup as described for Visit 2A and bring subject back in 24 hours to complete evaluation;
- Dispense study drug and instruct the subject to take one capsule every morning (with or without food) in the order indicated on the blister card ([Section 9.4.3](#)) and advise on lifestyle counseling. Subject should also be instructed to withhold dosing on the morning of the next scheduled study visit; and
- Schedule the next study visit in 4 weeks (28 ± 3 days).

10.3 Week 4 (Visit 3, End of Titration)

The following activities will take place at Week 4:

- Obtain body weight;
- Obtain vital signs (blood pressure, heart rate, respiration rate and temperature);
- Record any adverse events reported or observed;
- Record any changes in concomitant medications;
- Collect blood sample for limited chemistry panel;
- Perform a urine pregnancy test (WOCBP only) and remind subject about contraception. If the subject is pregnant, she will be withdrawn from study;
- Administer the final dose of study drug from the previous visit, collect previously dispensed drug, assess treatment compliance, and perform drug accountability (do not administer study drug if subject has taken a dose prior to coming in for this visit, and instruct the subject that for the next visit, they must not take their study drug until they arrive at the clinic);
- Contact EDC/RTSM to dispense study drug and instruct the subject on the proper use of the study drug (including withholding dosing on the morning of the next scheduled visit), and advise on lifestyle counseling;
- Schedule the next study visit in 4 weeks (28 ± 3 days).

10.4 Week 8/End of Study or Early Termination (Visit 4)

The following activities will take place at Visit 4A (first day of 2-day visit):

- Obtain body weight;
- Obtain vital signs (blood pressure, heart rate, respiration rate and temperature);
- Collect PK blood sample for assessment of phentermine and topiramate levels (prior to dosing);
- Record any adverse events reported or observed;

- Record any changes in concomitant medications;
- Perform a urine pregnancy test (WOCBP only) and remind subject about contraception;
- Set up 24-hr ABPM monitoring equipment;
- Collect study drug from previous visit, assess treatment compliance, and perform drug accountability;
- Administer last daily dose of study drug, record time of dosing, then initiate ABPM monitoring; and
- Provide subject with instructions for proper handling of ABPM device and remind the subject to return to the clinic in 24 hours to complete study.

The following activities will take place at Visit 4B (second day of 2-day visit):

- Record any adverse events reported or observed (note that as described in [Section 12.3](#) adverse events known to the investigator and occurring within 28 days after the last dose of study drug must be reported);
- Record any changes in concomitant medications;
- Perform a physical examination;
- End 24-hr ABPM monitoring, disconnect devices, and upload data upon verifying successful ABPM; if verification of successful ABPM cannot be made, repeat 24-hr ABPM setup as described for Visit 4A and bring subject back in 24 hours to complete evaluation;
- Perform 12-lead electrocardiogram (ECG);
- Obtain full blood chemistry, hematology, and urinalysis for laboratory testing;
- Obtain vital signs (blood pressure, heart rate, respiration rate and temperature); and
- Discontinue subject's study participation.

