8.3 Discontinuation of Study Drug and Subject Withdrawal

The Sponsor reserves the right to discontinue this trial at any time. The investigator must discontinue subjects from the study should any of the following occur:

- Any medical condition or circumstance that exposes the subject to substantial risk and/or does not allow the subject to adhere to the requirements of the protocol;
- Any serious adverse event (SAE), clinically significant adverse event (AE), severe laboratory abnormality, intercurrent illness, or other medical condition in which, in the judgment of the investigator, continued participation in the study is not in the best interest of the subject;
- Pregnancy;
- Subject elects to withdraw;
- Requirement for other medical treatment that is excluded by the protocol;
- Subject is unblinded by the investigator;
- Failure of the subject to comply with protocol requirements or study related procedures; or
- Termination of the clinical trial by the Sponsor or by FDA.

Reason(s) for subject withdrawals as well as details relevant to the subject withdrawal will be documented. If a subject is withdrawn from the clinical trial prior to trial completion, the subject will undergo all end of study procedures.

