12.4.3 Pregnancy

If any study subject becomes or is found to be pregnant while receiving the investigational product, the investigator must immediately discontinue study treatment and report the pregnancy to VIVUS or designee within 1 business day of learning of the pregnancy.

The investigator will follow the pregnancy until completion or until pregnancy termination (i.e., elective pregnancy termination) and then notify VIVUS or designee of the outcome. The investigator will provide this information as a follow-up to the initial pregnancy report.

For reported pregnancies that result in a live birth, the status of the newborn should be assessed at the time of birth. The status of an aborted fetus should be assessed by gross visual inspection, unless pre-abortion test findings are suggestive of a congenital anomaly.

If pregnancy outcomes meet the criteria for classification as SAEs (i.e., stillbirth, neonatal death, or congenital anomaly), the investigator should follow the procedures for reporting SAEs. Similarly, any pregnancy outcomes that are considered to be adverse events should be reported as such on the appropriate CRF. However, pregnancy in itself need not be reported as an adverse event if there is no associated adverse outcome.

For reporting purposes, ectopic pregnancies should be reported as SAEs, but because the fetus is not potentially viable, they need not be reported as a pregnancy.

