13.1.2 Method for Prevention and Treatment of Missing Values

For subjects who discontinue treatment prior to study completion, every attempt will be made to obtain end of study ABPM assessments prior to their discontinuation of treatment or initiation of changes to concomitant antihypertensive medications.

Several sensitivity analyses will be considered to explore any deviations from statistical assumptions and the impact of missing data on the conclusion of the primary analysis. The details of the sensitivity analyses will be included in the SAP.

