5.4 Per Protocol (PP) Population

PP Population will be comprised of ITT subjects who met all of the following criteria:

- Compliant to study treatment (defined as $\geq 80\%$ treatment compliance as specified in [Section 6.5](#));
- Last daily dose of study drug administered on the same date that ABPM was initiated at Visit 4A (first day of Week 8/End of Study or Early Termination);
- Had at least 23.5 hours of ABPM data (i.e. blood pressure and heart rate data) at baseline and at Week 8/End of Study or Early Termination, and at least 75% of 24-hr ABPM readings (or equivalently 48 readings during the 24-hr period) are not missing;
- Subjects with any major protocol deviation that had impact on ABPM readings will be excluded from the PP Population.

The PP population will be used to assess the primary and secondary endpoints as primary analyses. Subject inclusion in the PP population will be determined and documented prior to database lock and treatment unblinding.

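### The early-termination visit includes an unconditional dose of study drug, and Protocol 8.3 sends every withdrawn subject to it, while 12.4.3 requires treatment to stop at once in pregnancy; the passages must be reconciled

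*Protocol*

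**What the plan says.** Protocol 8.3 opens its list of reasons with "The investigator must discontinue subjects from the study should any of the following occur". Pregnancy, serious or clinically significant adverse events and unblinding are on the list. The section ends: "If a subject is withdrawn from the clinical trial prior to trial completion, the subject will undergo all end of study procedures". It makes no exception by reason.

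The end-of-study procedures are in Protocol 10.4, whose title covers Week 8, End of Study and Early Termination. Visit 4A includes "Perform a urine pregnancy test (WOCBP only) and remind subject about contraception" and, later in the same list, "Administer last daily dose of study drug, record time of dosing, then initiate ABPM monitoring".

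Protocol 12.4.3 says that on pregnancy "the investigator must immediately discontinue study treatment and report the pregnancy to VIVUS or designee". Protocol 10.3 says of a positive Week 4 test: "If the subject is pregnant, she will be withdrawn from study". For subjects who stop treatment early, Protocol 13.1.2 says "every attempt will be made to obtain end of study ABPM assessments prior to their discontinuation of treatment".

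The SAP makes the per-protocol (PP) population primary for efficacy (7.1, 7.2.1) and maps early-termination ABPM to Week 8 (7.2.1). SAP 5.4 requires at least 80% capsule compliance and "Last daily dose of study drug administered on the same date that ABPM was initiated at Visit 4A"; its wording extends this to Early Termination.

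**The concern.** A site that finds a positive test at Week 4 is told to withdraw the subject (10.3), to carry out all end-of-study procedures on a withdrawn subject (8.3), to give a dose as one of them (10.4), and to stop treatment immediately (12.4.3). No passage says which prevails. At Visit 4A the pregnancy test is listed before the dose, but the section does not say what a positive result means for the steps that follow.

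For serious adverse events, other adverse events and unblinding, no section contradicts 10.4 in such explicit terms. The protocol simply does not say whether the dosing step applies to a subject who is already off drug when the visit takes place.

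At stake first is subject safety and the site's ability to comply. Second, and much less, is the PP set: the dose given at the visit satisfies the criterion meant to show that the final recording was made on drug.

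**Working it through.** **1. Pregnancy: the passages side by side.**
- 10.1: positive test, no further screening procedures.
- 10.2: positive test, subject does not qualify.
- 10.3: positive test, subject withdrawn. This triggers 8.3.
- 8.3: withdrawn, so all end-of-study procedures.
- 10.4: those procedures include a dose; a positive test has no stated consequence.
- 12.4.3: treatment stops immediately.

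The authors wrote conditions elsewhere. Visit 3 withholds the clinic dose if one has already been taken that day. Protocol 9.6.2 (blood pressure rescue) and 9.6.3 (diabetes therapy) set out the order of final ABPM, end of treatment and exit. Pregnancy, serious adverse events and unblinding have no such sequence.

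**2. How many subjects.** Planned drop-out is 5% of 555 (Protocol 13.2, SAP 8): 0.05 × 555 = 27.75, about 28. This counts all drop-outs. Those recorded while still taking drug, as 13.1.2 intends, are not affected, nor are those who never return. So 28 is an upper bound, and the documents give nothing from which to estimate the actual number.

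**3. What the PP criteria let through.** SAP 6.5 compliance = 100 × capsules consumed / capsules planned while actively enrolled. The end of active enrolment is not defined; assume that it runs to the visit.
- Example: doses on Days 1 to 40, none on Days 41 to 50, one at an early-termination visit on Day 51. Compliance = (40 + 1)/51 = 80.4%, which passes. Last-dose date = ABPM start date, which passes. Time off drug: 10 days.
- One more missed day: 40/51 = 78.4%, which fails.
- Longest passing gap by visit day: Day 56, 11 days (45/56 = 80.4%; 44/56 = 78.6% fails); Day 42, 8 days (34/42 = 81.0%); Day 28, 5 days (23/28 = 82.1%); Day 14, 2 days (12/14 = 85.7%).
- If active enrolment instead ends at the decision to withdraw, the compliance rule sets no limit on the gap.

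**4. Effect on the primary comparison.** The plan's own figure first: SD 10 mmHg, difference 3 mmHg, two-sided alpha 0.05, power 80%. n = 2 × (1.960 + 0.842)² × 10² / 3² = 174.4, so 175 per group; 175/0.95 = 184.2, so 185. This reproduces the plan. The t-test form gives 176 before drop-out and 80.1% power at 176.

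Now suppose a share f of VI-0521 recordings follows a gap and carries no drug effect. Both f and the zero effect are assumptions. The difference becomes −3.0 × (1 − f), with t-test power at 176 per group:

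| f | Difference (mmHg) | Power |
|---|---|---|
| 1% | −2.97 | 79.4% |
| 2.5% | −2.93 | 78.1% |
| 5% | −2.85 | 76.0% |

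For non-inferiority with a true difference at the +3 mmHg margin, f = 5% shifts it by 0.15 mmHg. SE = 10 × √(2/176) = 1.066, and 0.15/1.066 = 0.141. The one-sided error is then Φ(−1.960 + 0.141) = Φ(−1.819), about 0.034 instead of 0.025. A share of 5% equals the whole planned drop-out, so it is an extreme.

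**The case against.** The strongest reply is that the dosing step describes the last of a run of daily doses and so presupposes a subject still taking drug. Protocol 9.6.2, 9.6.3 and 13.1.2 and SAP 7.1.7 all intend the final recording to come before treatment stops. For a subject handled that way, the Visit 4A capsule is the ordinary daily dose. Sections 8.3 and 12.4.3 already give pregnancy a consequence, and a sensible site would let them override a visit checklist. Section 10.3 also lists dosing and dispensing after its pregnancy bullet, and nobody would apply those to a subject just withdrawn.

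Much of this stands. A reader might infer that every early terminator is re-dosed, or that about 28 subjects are affected. The documents do not support that: the group is limited to subjects already off drug, or required to be. Nor does any passage direct a site to restart drug after an adverse event or unblinding; the text only fails to exclude it. The reply does not remove the pregnancy conflict. That the dosing step covers only subjects still on treatment, and that 12.4.3 prevails, are reasonable inferences, but neither is written down.

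On the endpoint, a reader might infer that a single-dose recording enters as the 8-week value. In the example it is 40 doses, a gap and one more dose. There are partial safeguards. Protocol 9.4.4 says the trough sample may be used to identify unacceptable compliance for PP analyses, although SAP 5.4 does not name it and SAP 7.2.4 only summarises it. The major-deviation review (SAP 5.4, 6.7) could exclude some cases, but no rule names this one. The SAP's treatment-policy strategy also means that using an observed value after an interruption is not plainly contrary to its estimand.

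**Conclusion.** The wording conflict is real. Read literally, 8.3, 10.4 and 12.4.3 cannot all be followed for a pregnant subject who is withdrawn, and 10.4 is the only visit section with a pregnancy test that gives no consequence of a positive result. For other subjects already off drug, the scope of the dosing step is unstated. This part needs no frequency estimate: one pregnancy is enough to bring it about. The number affected is unknown and at most about 28.

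The PP point is secondary and minor. The same-date criterion cannot tell continuous dosing from a gap followed by the visit capsule. The size of gap that passes depends on how active enrolment is defined. A reader might infer material bias in the primary result. The documents give no basis for that: under the assumed shares of 1% to 5%, power falls from 80.1% to between 79.4% and 76.0%, and the actual share is probably lower than the upper figure because that would need every planned drop-out to be such a case.

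**What to change.** **Protocol.** Reconcile 8.3, 10.4, 12.4.3 and 13.1.2. State in 10.4 which early-termination subjects the Visit 4A dosing step covers, and cross-reference there what follows a positive pregnancy test. The sponsor's clinicians decide which instruction governs; this review proposes no rule. Confine the change to the dosing step. A general exemption from end-of-study procedures would also remove the final ECG, laboratory tests, physical examination and ABPM from the subjects for whom they matter most.

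**SAP 5.4.** Add a clause that the same-date criterion also requires dosing to have been ongoing before Visit 4A, with the permitted gap defined before unblinding. State in 6.5 when active enrolment ends for the compliance denominator.

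**Cost.** A few sentences in the protocol and one or two clauses in the SAP. A few early-termination recordings would leave the PP set; they would remain in the ITT analyses.

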9.4.3 Administration

Investigators will instruct subjects to take 1 capsule of study drug every morning with or without food. Capsules must be taken whole, and should not be broken or split apart in any manner. When dispensing titration blister cards, investigators should ensure that subjects understand that each blister card contains a 4-week supply of study drug, and that the capsules must be taken in a specific order (i.e., Week 1 before Week 2, and Week 3 before Week 4).

When dispensing study drug bottles, investigators should ensure that subjects understand that each bottle contains a 4-week supply of study drug and that each bottle contains extra capsules that should only be taken for special circumstances (e.g. capsule is accidentally dropped and cannot be retrieved or subject cannot return to the end of study visit within window). Study drug will not be dispensed until the morning of Day 2 after the ABPM device is removed following the baseline 24-hr recording and data has been confirmed to be compliant.

Subjects will be instructed to withhold dosing of study drug on study visit days until after certain procedures are completed.

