7.1.5 Handling of Multiple Observations or Out of Window Observations

For efficacy data, if multiple assessments were recorded for the same protocol defined visit (e.g., same nominal visit but different time points or re-assayed), the later one or the re-assayed data will be used for data summary and analysis.

If a subject has a scheduled visit, the assessment obtained at the scheduled visit will be used for data summary and analysis. Otherwise, if no scheduled visit assessment exists but unscheduled visit assessments are available within the visit window, the data from the latest unscheduled visit will be used for statistical analysis.

Regarding the visit windows that will be applied to handle multiple observations and unscheduled visits, Table 7-1 shows the protocol-defined visit windows and the data analysis visit windows. Protocol-defined visit windows are usually more stringent to ensure study better adherence to study schedule; however, it could be too narrow for inclusion of unscheduled visits for data analysis. In order to include study data collected from any unscheduled visits, the analysis time windows will be widened for visit attribution. Note that data collected from an unscheduled visit that is out of the time window will not be included in data analysis, but will be provided in listings.

Table 7-1 Analysis Visit Window

Visit Number	Visit Name	Study Week	Target Study Day ^[1]	Protocol-Defined Time Window	Time Window to Attribute Unscheduled Visit to Analysis Visit
1	Screening	Week -4	-28	--	--
2A	Baseline/Randomization	Week 0	-1	+3 days	The last measurement prior to receiving the 1 st randomized dose

Visit Number	Visit Name	Study Week	Target Study Day ^[1]	Protocol-Defined Time Window	Time Window to Attribute Unscheduled Visit to Analysis Visit
2B	Baseline/Randomization	Week 0	1	--	--
3	End of Titration	Week 4	28	±3 days	-3 and +6
4A	End of Study or Early Termination	Week 8	56	±3 days	Week 7 to all visits before or on the last study dose date
4B	End of Study or Early Termination	Week 8	57	--	All visits after the last study dose date

[1] Study day 1 is defined as the date of the first dose for each subject.

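### The per-protocol dosing criterion is tied to Visit 4A, not to the Week 8 ABPM recording analysed, and the plan leaves the dosing, coding and selection of a repeat recording open

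*Protocol*

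**What the plan says.** At Visit 4A (Protocol 10.4) the site sets up the equipment and takes back the drug: "Collect study drug from previous visit, assess treatment compliance, and perform drug accountability". The next step is "Administer last daily dose of study drug, record time of dosing, then initiate ABPM monitoring". At Visit 4B, if the recording cannot be verified, the instruction is: "if verification of successful ABPM cannot be made, repeat 24-hr ABPM setup as described for Visit 4A". The subject then returns 24 hours later. The 4B list contains no dosing or dispensing step. Protocol 9.4.3 notes that "each bottle contains extra capsules that should only be taken for special circumstances"; a repeat recording is not among its examples.

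SAP 5.4 makes this a condition for the per-protocol population: "Last daily dose of study drug administered on the same date that ABPM was initiated at Visit 4A". SAP 7.1 makes that population primary for efficacy.

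SAP 7.1.5 has two selection rules. For several assessments at one protocol-defined visit, "the later one or the re-assayed data will be used for data summary and analysis". Where a scheduled visit exists alongside unscheduled ones, "the assessment obtained at the scheduled visit will be used for data summary and analysis". Table 7-1 limits the attribution of unscheduled visits to 4A to "Week 7 to all visits before or on the last study dose date" and sends visits after the last dose date to 4B. Neither document says which rule governs a repeat recording that the protocol itself directs.

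**The concern.** A criterion that links dosing to ambulatory monitoring is useful only if it examines the recording that supplies the endpoint. Here it examines the date of the first attempt, even when that attempt failed and a later one is analysed. The major-deviation exclusion in SAP 5.4 does not help, because a repeat done as Protocol 10.4 directs is not a deviation.

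The primary question is whether VI-0521 raises 24-hour SBP, judged against a 3 mmHg margin. If some analysed recordings were made beyond the once-daily dosing interval and the drug effect had partly worn off, a true pressor difference from placebo would be diluted towards zero. In a non-inferiority test that error favours the sponsor's conclusion. The ITT sensitivity analyses would not reveal it, since the same recording-selection rules in SAP 7.1.5 apply to all efficacy data.

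**Working it through.** **1. What the text yields on a repeat day.** Two matters are open: whether a dose precedes the repeat, and how the repeat is coded.

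| Repeat coded as | New dose? | Recording used (SAP 7.1.5) | Last-dose date vs 4A start date | SAP 5.4 dosing criterion |
|---|---|---|---|---|
| Same visit | No | Repeat, about 24–48 h after last dose | Same | Met |
| Same visit | Yes | Repeat, about 0–24 h after dose | One day later | Not met |
| Unscheduled | No | First (4A) recording | Same | Met |
| Unscheduled | Yes | First (4A) recording | One day later | Not met |

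In the first two rows the criterion keeps the undosed repeat and removes the dosed one. In the fourth it removes a subject whose analysed recording did follow a dose. In the last two rows the first recording must still meet the SAP 5.4 completeness rules.

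**2. A usable first recording can be displaced.** The schedule in SAP 7.1.4 gives 16 h × 3 + 8 h × 2 = 64 readings. SAP 5.4 requires 75%: 0.75 × 64 = 48, as the SAP states. The site check in Protocol 11.4 requires 80%: 0.80 × 64 = 51.2, so 52. A 4A recording with 48 to 51 readings and at least 23.5 h of data is complete enough for the per-protocol population, yet triggers a repeat that may replace it.

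**3. The plan's sample size.** Inputs (Protocol 13.2, SAP 8): SD 10, difference or margin 3 mmHg, two-sided 0.05 (one-sided 0.025), power 80%, dropout 5%.

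n = 2 × (10/3)² × (1.960 + 0.842)² ≈ 174.4, so 175 per group; 175/0.95 = 184.2, so 185. The stated figure reproduces (the exact t-test needs 176, which inflates to 186). It is not in dispute.

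**4. Illustration of dilution, VI-0521 against placebo.** The documents give no repeat rate and no loss of effect, so both are assumptions.

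- Attenuation = (share of analysed recordings that are undosed repeats) × (share of effect lost).
- Evaluable per group: 185 × 0.95 ≈ 176. SE = 10 × √(2/176) = 1.066.
- Chance of a false non-inferiority claim = Φ((3 − δ)/1.066 − 1.96), where δ is the diluted difference.

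| True difference | Attenuation | δ | Chance of false claim |
|---|---|---|---|
| 3.0 | none | 3.00 | 2.5% |
| 3.0 | 0.10 × 0.5 = 5% | 2.85 | Φ(−1.82) = 3.4% |
| 3.0 | 0.20 × 1.0 = 20% | 2.40 | Φ(−1.40) = 8.1% |
| 4.0 | none | 4.00 | 0.2% |
| 4.0 | 20% | 3.20 | 1.6% |

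**5. Superiority.** With a true −3 mmHg, exact t-test power at 176 per group is 80.1%. If 5% of recordings are undosed repeats that lose 25% to 100% of the effect, power is 79.1% to 76.0%. Over 2% to 15% of recordings it is 79.7% to 66.5%.

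**The case against.** A reader might infer that the plan sends off-drug recordings into the primary analysis and so biases it towards non-inferiority. The documents do not support that much, for four reasons.

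- **The dose may carry over.** At 4A, monitoring is started only within the dosing step; the set-up step alone starts nothing. The reference back to 4A can fairly be read to include both. The bottle holds 35 capsules, spares included, and both schedules list drug accountability at 4B as well as 4A. Against this, the drug is collected at 4A and 4B lists no dose. The text is unclear, and either reading leaves the criterion misfiring.
- **There is a partial safeguard.** An undosed repeat coded as unscheduled would give way to the scheduled recording, and Table 7-1 would send it to 4B. This stands, but only under that coding, which the plan does not specify.
- **Off-drug is not shown.** The documents give no half-life or offset data. They use a pre-dose trough sample to assess compliance, topiramate is extended-release, and the rationale ties some blood-pressure improvement to weight loss, which a day without drug would not undo. Complete loss of effect is an extreme assumption for VI-0521.
- **The direction is not uniform.** Dilution is conservative for superiority over placebo. Against phentermine both arms are affected, so the net effect depends on the unknown loss in each. At a true 4 mmHg difference, even 20% attenuation leaves the false-claim rate at 1.6%, below the nominal 2.5%.

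**Conclusion.** The defect is in the rule. SAP 5.4 does not test the recording that supplies the primary endpoint. Protocol 10.4 is silent on dosing before a repeat, and SAP 7.1.5 gives two answers on which recording counts. Under same-visit coding the criterion retains an undosed repeat and excludes a dosed one.

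Bias in the primary result is possible but not established, and its size is unknown. The figures of 3.4% and about 8% hold only at a true difference equal to the margin, with SD 10, 176 per group, dilution confined to the active arm in the placebo comparison, and assumed repeat and loss rates; the second is an extreme case. The sample size is unaffected. This is an inexpensive correction that should be made, not a reason to doubt the design.

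**What to change.** 1. Reword the SAP 5.4 criterion to require study drug on the same date as the start of the Week 8 ABPM recording used in the analysis.
2. State in SAP 7.1.5 and Table 7-1 how a protocol-directed repeat is coded and which recording is used, including when the first has 48 to 51 readings.
3. Flag every analysed recording that starts after the last dose date, and run one sensitivity analysis of the primary endpoint without them.
4. Reconcile Protocol 10.4, SAP 5.4 and SAP 7.1.5 on what happens on a repeat day. No dosing rule is proposed here.

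Cost: a few sentences in the SAP, a protocol clarification, one derived flag and one extra model run. The flag needs the last-dose date, which SAP 6.5 already requires for exposure; any dose given on a repeat day must therefore be captured. The downside is that a few repeat recordings may drop out of the per-protocol population.
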